### **6.2.5 Physical Examinations**

Physical examinations will be performed in accordance with the Schedule of Procedures (Table 5).

A physical examination covering the major body systems (general appearance, head [ear, nose and throat], cardiovascular, eyes, respiratory, abdomen, urogenital, musculoskeletal, neurological, lymph nodes and skin) will be performed at screening (baseline), last day at ICU and at D28 (or when patient withdraws from the study prior to D28).

At screening the physical examination will also include:

- Predicted body weight (PBW). Calculate the PBW (kg) using the following formulae:  
For men:  $50 + 0.91(\text{height in cm} - 152.4)$   
For women:  $45.5 + 0.91(\text{height in cm} - 152.4)$
- Actual height (in cm). The patient's height does not need to be measured immediately if recorded elsewhere in the medical records or provided 'anecdotally' by relatives (the PBW can then be calculated as described above).

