### ***5.2.1 Admission***

At Admission to the ICU they include details of: Status including Intubation, Renal support, Body position and any required Vasoactive infused drug treatment.

These are then supported by a combined assessment of Acute physiology and Chronic health to derive an APACHE II score (0-71) to additionally classify the severity of the condition.

Demographics (Age, Race, Sex) are then supplemented with details of the Disease diagnosis and Aetiology supported by Imaging (Chest X-ray / CT scan) and Ventilation evidence (Gas exchange variables). Aetiology is categorised as: Pancreatitis, Trauma/Burns, Sepsis, Multiple Transfusion, Aspiration, Pneumonia or Other. If the cause is Sepsis then the site of infection is noted.

Following satisfactory completion of all the Inclusion/Exclusion criteria details (including a negative pregnancy test for females) Medical history (including any relevant previous and ongoing medical conditions) is recorded together with Prior medications (taken in the last 30 days but stopped before signing Informed consent) and a complete Physical examination (with predicted body weight).

Ongoing medications are recorded as Concomitant Medications (classified as either Bolus or Infusion) and reported accordingly if started prior to treatment dosing (Day 1). Any medication given with or after the first injection of study drug is also classified as a concomitant treatment.

Prior to the start of dosing on Day 1 the Patient status and Inclusion/Exclusion criteria are confirmed and all Medications are updated.

A series of Baseline safety assessments are then performed. These include: Safety laboratory tests (Biochemistry, Haematology, Urinalysis), Vital signs, 12 Lead ECG and Ventilation (Gas exchange). Specific variables measured are listed in section 5.8.

Baseline efficacy assessments performed are: the System Organ Failure SOFA score and Quality of Life (EQ-5D-3L) assessment. Details of the specific variable items measured are given in section 5.3.3.5 and 5.4.2 respectively.

Pre-dose blood samples are taken for pharmacodynamic baseline assessment. These include: Myxovirus Resistance Protein A (MxA), CD 73 biomarker, Potential Inflammatory Markers (PIMs). Also a sample for Anti Drug Antibodies (ADA) and Neutralising Antibodies (NABs) to Interferon Beta-1a assessment will be taken. A tier based approach for the NABs analyses will be used where NABs will be assessed only if ADAs exists.

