#### ***6.2.4.5 Sequential Organ Failure Assessment (SOFA) Analysis***

Total scores and Change from baseline scores (Day 1 Pre-dose) assessed daily up to Day 14 and then at Day 21 and Day 28 (In or Out of the ICU) or Early Termination, together with the derived Last observation performed will be numerically summarised according to Treatment group (FP-1201-lyo/Placebo), Severity of ARDS (Moderate/Severe) and Overall using the FAS population. Separate supporting summaries by Country will be included.

The contributing Cardiovascular, Respiratory, Coagulation, Hepatic, Renal and CNS organ sub scores will be similarly presented.

The Total SOFA score at the Last observation performed will be analysed using an Analysis Of Covariance (ANCOVA) model (Ref 8) this will use change from baseline as the response variable and will include Treatment group (FP-1201-lyo/Placebo), Severity of ARDS (Moderate/Severe) and Country (1-8) as fixed effect factors. The Baseline value will also be used as a covariate term in the model.

Model assumptions of normality and constant variance will be investigated and if necessary an alternative model or data transformation will be substituted.

Model estimates (LS means and a 95% confidence interval for the treatment difference) will be presented. Homogeneity of treatment effect will be assessed by obtaining the difference in LS means together with 95% confidence intervals for the categories of ARDS severity using the ANCOVA model with the addition of a treatment by ARDS severity interaction term and displaying these in a Forest Plot.

Sub scores will not be analysed.

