### ***6.2.5.3 Respiratory And Neurological Function Assessment***

#### ***6.2.5.3.1 Respiratory Function (FEV-1) Analyses***

FEV-1 measured at Day 180 and Day 360 will be numerically summarised using actual values by Treatment group (FP-1201-lyo/Placebo), Severity of ARDS (Moderate/Severe) and Overall for each assessment time using the FAS population only. Again this group will only include survivors at the time of assessment. Separate supporting summaries by Country will not be included.

The FEV-1 will be analysed using an ANCOVA model (as for the Total SOFA scores in Section 6.2.5.5 but excluding the baseline covariate).

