#### ***6.2.5.3.2 Neurological Function (6MWT) Analyses***

6MWT distances recorded at both Day 180 and Day 360 will be numerically summarised using actual values by Treatment group (FP-1201-lyo/Placebo), Severity of ARDS (Moderate/Severe) and Overall for each of the performed tests (Test One/Test Two). They will also be summarised according to the furthest distance walked during Test One or Test Two as recommended by the 6MWT guidelines (Ref 11). Separate summaries by Country will not be included.

These will involve patients from the FAS population who survive up to the time of assessment.

In line with the guidelines the furthest distance walked during the two tests will be analysed using an ANCOVA model (similar to the Total SOFA scores in Section 6.2.5.5 excluding the baseline covariate). As described in Section 5.4.3.2, in cases where only one result is collected this will also be used as the best result (furthest distance walked). The value of inclusion of additional Pre-Test covariates such as Walking limitations, Supplemental Oxygen use, SP02, Dyspnoea or Fatigue will be explored.

In addition, the distance walked during Test One will also be performed as a supplemental analysis in case there is a disproportionate number of patients across the two treatment groups who refuse or who are unable to perform the second test and which may lead to inconsistent inclusion of a possible 'learning effect'.

As the 6MWT is likely to only be performed in what is effectively a selective subgroup of patients (i.e.: those who survive) the results will be assessed in conjunction with the mortality rates in the two treatment groups. The LS mean and the 95% confidence interval for the treatment difference in those LS means will therefore only be presented Overall.

All other measures will only be summarised.

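### The main 6MWT model, and the FEV1 model if FEV1 is a volume, omit age, sex and height; the 6MWT covariates to be explored are post-randomisation

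*SAP*

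**What the plan says.** For FEV1, SAP 6.2.5.3.1 states: "The FEV-1 will be analysed using an ANCOVA model (as for the Total SOFA scores in Section 6.2.5.5 but excluding the baseline covariate"). For the walk test, SAP 6.2.5.3.2 has the "furthest distance walked during the two tests will be analysed using an ANCOVA model (similar to the Total SOFA scores in Section 6.2.5.5"), again without the baseline term. The SOFA model is in SAP 6.2.4.5 and has "Treatment group (FP-1201-lyo/Placebo), Severity of ARDS (Moderate/Severe) and Country (1-8) as fixed effect factors" plus the baseline value. With that value removed, treatment, severity and country remain. SAP 7.2.5.3.1 and 7.2.5.3.2 accordingly call the outputs ANOVA estimates.

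For the walk test only, the SAP adds: "The value of inclusion of additional Pre-Test covariates such as Walking limitations, Supplemental Oxygen use, SP02, Dyspnoea or Fatigue will be explored". SAP 5.4.3.2 places these recordings immediately before each test, at D180 and D360.

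On baseline data, SAP 5.2.1 says "Demographics (Age, Race, Sex) are then supplemented with details of the Disease diagnosis and Aetiology". Height is obtained at screening (Protocol 6.2.5, SAP 5.8.3). SAP 5.9.5 lists age, sex and weight (BMI), among others, for blinded review, and puts the variables so identified into models that test robustness. The list is open-ended, but height is not on it.

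On the analysed set, SAP 6.2.5.3.2 says: "These will involve patients from the FAS population who survive up to the time of assessment". Protocol 8.5.2.5 makes the D180 comparisons descriptive.

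**The concern.** Neither endpoint has a baseline measurement, so the usual source of precision in an ANCOVA is missing. The natural substitutes are prognostic variables fixed before treatment. The protocol's appendix (reference equations for 6MWD) names height, age, sex and weight among factors that may affect walking distance in healthy adults, and SAP 5.9.5 itself says that adjustment gains precision in proportion to correlation with outcome. Yet the main models use none of these variables.

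The extra covariates that the SAP does mention for the walk test are measured months after a 6-day treatment. If treatment improves breathlessness, fatigue or oxygenation and these affect walking distance, conditioning on them removes part of the effect of interest. The SAP gives no selection rule. The blinded review precedes the D90 lock and the overall code is broken after D90 (Protocol 5.4), so this exploration could take place with treatment codes known.

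At stake are the width of the reported intervals and the meaning of any adjusted estimate.

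**Working it through.** **No planned figure to reproduce.** The documents give no SD, R², sample size or precision target for FEV1 or 6MWD. The only sample-size calculation (272 evaluable patients, Protocol 8.10) concerns VFDsurv and has no bearing here.

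**1. Precision.** Let R² be the share of variance left after severity and country that age, sex and height explain. The standard error is multiplied by √(1 − R²), and the unadjusted interval is 1/√(1 − R²) times as wide as the adjusted one. R² of 0.1 to 0.5 is an assumption.

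| R² | SE multiplier | SE reduction | Unadjusted interval wider by | Equivalent patients, 1/(1 − R²) |
|---|---|---|---|---|
| 0.1 | 0.95 | 5% | 5% | 1.11 |
| 0.3 | 0.84 | 16% | 20% | 1.43 |
| 0.5 | 0.71 | 29% | 41% | 2.00 |

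**2. In metres, for 6MWD.** The 95% half-width is 1.96 × SD × √(4/n). At the planned D28 mortality of 30% and 15%, 300 randomised patients leave 150 × 0.70 + 150 × 0.85 = 232.5 survivors at D28. Fewer will be tested at D180, so n of 100 to 200 is assumed, with SD 80 to 140 m (also assumed).

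- Mid case, SD 110 m and n = 150: 1.96 × 110 × √(4/150) = 35.2 m as planned. After adjustment it is 33.4 m (R² 0.1), 29.5 m (0.3) or 24.9 m (0.5).
- Range: from 22.2 m (SD 80, n = 200) to 54.9 m (SD 140, n = 100) as planned; 18.6 m to 45.9 m at R² 0.3.

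For scale, the protocol's appendix gives 30 m as the minimal important difference in chronic respiratory disease.

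**3. Cost if the covariates explain nothing.** The planned model has 10 parameters (intercept, treatment, one for severity, seven for eight countries). Three more at n = 150 inflate the SE by roughly √(140/137) = 1.01, about 1%.

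**4. Adjusting for a pre-test measure.** Take a true total effect of 30 m, and let treatment shift the pre-test measure by 0.4 of its within-arm SD. If that measure carries a fraction m of the effect, the adjusted coefficient is (1 − m) × 30. Suppose also that an unmeasured cause has loading 0.5 on the measure and lowers distance by 20 m per unit. The slope on the measure then moves by −20 × 0.5 = −10 m per SD, and the treatment coefficient by a further −10 × 0.4 = −4 m. All these values are illustrative.

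| m | Formula | Simulated | With shared cause, formula | Simulated |
|---|---|---|---|---|
| 0.25 | 22.5 | 22.7 | 18.5 | 18.8 |
| 0.50 | 15.0 | 15.2 | 11.0 | 10.9 |
| 0.75 | 7.5 | 7.1 | 3.5 | 3.4 |

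The simulation used 200 patients and 2,000 runs. Adjusting instead for a baseline prognostic variable left the estimate at about 30 m and reduced its standard error, for example from 13.8 to 11.2 m.

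**5. FEV1.** Protocol 6.1.2.6 describes FEV1 as a volume exhaled in the first second; SAP 5.4.3.1 describes it as a percentage of forced vital capacity. Step 1 can be argued for a volume, which depends on body size. It cannot be assumed for a ratio of two volumes.

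**The case against.** The strongest reply has five parts.

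- **The specified walk-test analysis is not biased.** The SAP undertakes only to explore the pre-test covariates, and its output section lists no table adjusted for them. This stands. A reader might infer that the planned 6MWT estimate is distorted; it would be only if an explored model were reported as the treatment effect.
- **FEV1 has no symptom covariates.** This stands. SAP 6.2.5.3.1 proposes none, so that half of the point applies to the walk test alone.
- **Oxygen use and walking aids are test conditions.** The appendix says supplemental oxygen and wheeled walkers have an important effect on distance. That is a fair reason to record and tabulate them. However, its advice to hold them constant concerns repeat tests, and in a comparison of randomised arms they remain post-treatment variables.
- **SAP 5.9.5 already covers baseline variables.** In part. It would be wrong to say that age and sex are ignored, but they can enter only sensitivity models, and the main estimates stay unadjusted.
- **The size is assumed and the analyses are descriptive.** Both stand. The appendix gives no R² and speaks of healthy adults. Neither endpoint is in the testing hierarchy of either document. Intervals are nevertheless the reported result, so their width matters.

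**Conclusion.** The point holds for the main 6MWT model: three collected, pre-treatment variables that the protocol's own appendix names are left out. The likely gain is a standard error smaller by 5% to 29% over an assumed R² of 0.1 to 0.5. For FEV1 it holds only if the endpoint is a volume; for a percentage of forced vital capacity no gain is established.

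The pre-test measures are a risk confined to the walk test. A model containing them answers a different question from the total treatment effect. The 30 m illustration shows the direction, not a prediction.

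Two further inferences should be resisted. A much larger gain, such as a 37% reduction at R² 0.6, has no support in the documents. Nor does baseline adjustment repair the selection caused by different survival in the arms: it addresses only imbalance in the measured variables. The SAP already says the walk-test results must be read with the mortality rates. No formal error rate is affected.

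**What to change.** 1. In SAP 6.2.5.3.2, add age, sex and height as prespecified covariates in the main 6MWT ANCOVA, for both the furthest distance and the Test One analysis.
2. Reconcile the FEV1 definitions in Protocol 6.1.2.6 and SAP 5.4.3.1. If FEV1 is analysed as a volume, add the same covariates in SAP 6.2.5.3.1.
3. Use walking limitations, oxygen use, SpO2, dyspnoea and fatigue descriptively, by arm. Otherwise, label any model containing them as exploratory and as not estimating the total treatment effect.
4. Correct the cross-references: the SOFA ANCOVA is in SAP 6.2.4.5, whereas 6.2.5.5 is ventilation-free survival at Day 90.

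The cost is SAP wording, three degrees of freedom and a rule for missing height. Protocol 6.2.5 allows relatives to supply height informally, so the SAP should say how such values are handled. No new data are needed.

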#### ***6.2.5.4 Study Completion / Unblinding***

Long term and Extended follow up completion details reported at Day 180 and Day 360 respectively will be categorically summarised by Treatment group, Severity of ARDS and Overall for the FAS population according to whether the Patient has withdrawn (Yes/No) and the Primary Reason for termination. All other reasons will be listed.

A supporting Unbinding (Yes/No) categorical summary will be provided and all details listed.

#### ***6.2.5.5 Ventilation Free Survival At Day 90 Analyses***

Ventilation Free Survival at Day 90 will be classified as Dead, Alive-On Ventilator or Alive-Breathing Unassisted and summarised according to Treatment group (FP-1201-lyo/Placebo), Severity of ARDS (Moderate/Severe) and Overall. Separate supporting summaries by Country will be included.

A Cochran-Mantel-Haenszel hypothesis test including the stratification levels will be used to compare the two treatment groups. Statistical significance (p-values) obtained for the Overall group will be displayed with the categorical summaries.

#### ***6.2.5.6 Mortality At Day 90***

Overall mortality through to Day 90 (and subsequently to Day 180 and Day 360) will be displayed using Kaplan Meier survival plots and analysed using the logrank test.

Kaplan Meier product limit estimators of survival, together with median survival times (with 95% confidence intervals) for each treatment group will be presented.

The distributions will be compared for differences in rates between the two treatment groups (FP-1201-lyo/Placebo) with the stratified logrank hypothesis test (stratified by ARDS severity and country). The adjusted hazard ratio, obtained by fitting a Cox PH model containing both ARDS severity and country as factors in the model will be presented with 95% confidence intervals

Sensitivity analysis may be performed to assess the impact of censoring in the event of missing data due to withdrawal due to adverse events, efficacy, investigator decision or loss to follow up and also due to withdrawal of consent (as detailed on the Day 180/Day 360 Patient Status CRF page).

Homogeneity of treatment effect will be assessed by obtaining hazard ratios and associated confidence intervals by ARDS severity and by country and displaying these in a Forest Plot (log scale) using the Cox PH model with the addition of treatment by ARDS severity and treatment by country interaction terms.

Mortality at Day 180 and Day 360 will be similarly assessed as part of the Addendums for the Long Term and Extended Follow Up Reports, respectively (see Section 6.4).

### **6.2.6 Pharmacoeconomic Analysis**

Numerical summaries of overall costs and according to cost item for the UK will be by Treatment group (FP-1201-lyo/Placebo) and Severity of ARDS (Moderate/Severe) using the FAS population. NB: Separate summaries by other countries may be included later.

A cost-effectiveness analysis (Ref 9) to compare treatment with FP-1201-lyo to standard care (Placebo control) will involve an Analysis Of Variance (ANOVA) model. The total individual patient cost of treatment whilst in the ICU will be the response variable and Treatment group (FP-1201-lyo/Placebo), Severity of ARDS (Moderate/Severe) and Country (if available) will be included (without interactions) as fixed effect factors.

The total cost will be logarithmically transformed prior to analysis as the data distribution is likely to be truncated and positively skewed. The model fit and assumptions (particularly residuals) will be carefully assessed to ensure that the model is adequate and therefore provides reliable estimates.

Resulting model parameters for Treatment (FP-1201-lyo and Placebo) will be back transformed (exponentiated) to obtain geometric mean estimates (including 95%CI) of the total cost of each treatment and similar transformation of the treatment difference (FP-1201-lyo - Placebo) will allow expression of the difference in costs as a ratio (FP-1201-lyo relative to Placebo (%)) with 95% confidence limits.

In the event of model failure a non-parametric bootstrap procedure (Ref 10) will be substituted which involves repeated resampling from the available data to obtain estimates of the mean treatment costs together with 95% confidence intervals (using 2.5 and 97.5 percentiles from the resulting distribution).

A supplemental Incremental Cost Effectiveness Ratio (ICER) plot may also be presented for each Treatment group using the primary efficacy endpoint (VFDsurv) vs total cost of treatment for each individual patient.

This quadrant plot will identify both increasing and decreasing utility of the treatment cost with those of treatment efficacy

As discussed, these summaries will be presented with the Day 180 and/or Day 360 long-term follow up reports.

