## **8.7 Pharmacoeconomics**

The expected incremental cost-effectiveness will be calculated for intravenous FP-1201-lyo compared with standard care in the treatment of patients with moderate or severe ARDS admitted to ICU in the study-related countries. Criteria that will be measured at D28 as part of the cost-effectiveness analyses in this study are:

- Days free of organ failure (D28 or last day in ICU if patient has left the ICU earlier than D28, or at withdrawal)
- Days free of renal support
- Days free of vasoactive support
- Days free of mechanical ventilation
- Number of ICU-free days

- Number of days in hospital

Details on the statistical analysis of these criteria and their role in the economic evaluation will be provided in the SAP.

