#### ***7.2.6 Pharmacoeconomic Analysis***

Numerical summaries of overall costs and according to cost item will be presented together with ANCOVA analysis of logarithmically transformed costs. Numeric summaries will display actual values by Treatment group (FP-1201-lyo/Placebo), Severity of ARDS (Moderate/Severe) and Overall for the UK and by country if other country data become available (Tables 14.2.24.1,

Figures 14.2.13.1 and 14.2.13.2). Parameter estimates will also be presented after back transformation to obtain geometric mean estimates overall (Table 14.2.24.2).

A supplemental Incremental Cost Effectiveness Ratio (ICER) plot may also be presented for each Treatment group using the primary efficacy endpoint (VFDsurv) vs total cost of treatment for each individual patient (Figure 14.2.13.3).

As discussed, these summaries will be presented with the Day 180 and/or Day 360 long-term follow up reports to expedite the publication Day 90 statistical and clinical study reports.

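### The cost analysis reports geometric mean costs and their ratio, so it does not deliver the incremental cost-effectiveness that the protocol promises

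*SAP*

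**What the plan says.** Protocol 8.7 sets the aim: "The expected incremental cost-effectiveness will be calculated for intravenous FP-1201-lyo compared with standard care". It leaves the statistical detail to the SAP.

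SAP 6.2.6 defines the outcome: "The total individual patient cost of treatment whilst in the ICU will be the response variable". It fits an ANOVA with treatment, ARDS severity and, if available, country (SAP 7.2.6 calls the model ANCOVA). On scale it says: "The total cost will be logarithmically transformed prior to analysis". The treatment parameters are then "back transformed (exponentiated) to obtain geometric mean estimates (including 95%CI) of the total cost of each treatment", and the treatment contrast "will allow expression of the difference in costs as a ratio (FP-1201-lyo relative to Placebo (%)) with 95% confidence limits". SAP 7.2.6 confirms the output: "Parameter estimates will also be presented after back transformation to obtain geometric mean estimates overall".

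Arithmetic means enter the inference by one route only: "In the event of model failure a non-parametric bootstrap procedure (Ref 10) will be substituted". That procedure is to "obtain estimates of the mean treatment costs together with 95% confidence intervals". It names no between-arm difference.

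The only output labelled as an incremental cost-effectiveness ratio (ICER) is an optional plot, by arm, of each patient's VFDsurv against that patient's total cost. VFDsurv scores a death as -1 (Protocol 8.5.1.2).

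**The concern.** Incremental cost-effectiveness is a difference in expected cost divided by a difference in expected effect. Expected cost is the arithmetic mean, because the mean multiplied by the number of patients gives the total bill. A geometric mean does not have that property.

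The planned model gives neither the arithmetic mean nor a difference. Its ratio matches the mean ratio only when log costs have the same shape and spread in both arms. A drug that changes survival and time on support may well change the spread. The plot does not fill the gap. An incremental ratio is a contrast between arms, not a scatter of patients within each arm, and -1 is a rank code for death rather than a quantity of effect. SAP 6.2.3.2 itself leaves means and standard deviations out of the VFDsurv summaries.

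At stake is whether the health-economic result can be used for its stated purpose. Neither the primary endpoint nor safety is affected.

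**Working it through.** **No cost figure to reproduce.** SAP Table 4 gives every unit cost as to be confirmed. Any cost spread is therefore an assumption, and the check uses the protocol's planning distribution.

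**Step 1. Rebuild the planning scenario** (Protocol 8.10 and Table 6, row 15%/30% mortality with a 3.0-day difference).
- Control: 30% dead, 20% alive with zero ventilator-free days (VFDs), the other 50% spread evenly over 1 to 28 days. 0.50/28 = 1.8% per value, as in Table 6.
- Active: 15% dead, 14% alive with zero VFDs, the other 71% spread evenly. 0.71/28 = 2.5% per value, as in Table 6.
- Mean VFDs with deaths as 0 (1 + ... + 28 = 406): 406 x 0.50/28 = 7.25 and 406 x 0.71/28 = 10.30. The difference is 3.05 against the stated 3.0; the 14% is rounded, and 14.3% gives exactly 3.0.

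**Step 2. Turn this into a cost.** Assume cost is proportional to ventilated days, 28 minus VFDs (the days-of-use rule in SAP 5.5). Deaths have 0 days free (SAP 5.3.3.2) and so count as 28 days. A floor of 1 day keeps the logarithm defined. The survivor values 27, 26, ..., 1 and the floored 1 sum to 379; their logs sum to 64.56; ln 28 = 3.332.

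| | Active | Control | Ratio | Difference |
|---|---|---|---|---|
| Arithmetic mean | 0.29 x 28 + (0.71/28) x 379 = 17.73 | 0.50 x 28 + (0.50/28) x 379 = 20.77 | 0.854 | -3.04 |
| Geometric mean | exp(0.29 x 3.332 + (0.71/28) x 64.56) = 13.51 | exp(0.50 x 3.332 + (0.50/28) x 64.56) = 16.76 | 0.806 | -3.25 |

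The log-scale SDs are 0.91 and 0.83. The planned ratio shows a saving of about 19% where the mean saving is about 15%. With 14.3% in place of 14%, the ratios are 0.856 and 0.809.

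**Step 3. Add a cost common to both arms.** Ventilation is one of six cost items (SAP 5.5). Suppose every patient also incurs a fixed cost, in ventilated-day equivalents (assumed):

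| Common cost | Log-SDs | Mean ratio | Geometric mean ratio | Gap |
|---|---|---|---|---|
| 0 | 0.91, 0.83 | 0.85 | 0.81 | 0.05 |
| 6 | 0.50, 0.47 | 0.89 | 0.87 | 0.01 |
| 10 | 0.40, 0.38 | 0.90 | 0.89 | 0.01 |

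Gaps are taken before rounding (0.048, 0.015, 0.009). The direction is the same throughout.

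**Step 4. Equal spread does not supply the missing quantity.** For lognormal costs, mean = exp(mu + s²/2) and geometric mean = exp(mu). With the same s in both arms the two ratios agree, but the difference in geometric means is exp(-s²/2) times the mean difference: 0.92, 0.84, 0.73 and 0.61 of it at s = 0.4, 0.6, 0.8 and 1.0.

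**Step 5. The death code in the plot.** Scoring deaths as -1 instead of 0 shifts the between-arm mean effect by (0.30 - 0.15) x 1 = 0.15 day, about 5% of the planned 3.0 days.

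**The case against.** The strongest defence is that the SAP guards itself. Section 6.2.6 requires the fit and residuals to be checked. Unequal log-scale spread, which drives the two ratios apart under lognormal costs, breaches the constant-variance assumption and could lead to the bootstrap of means. Arithmetic means are also reported: SAP 6.1 includes mean and SD in summaries of continuous data, so a reader could see equal means beside an unequal ratio. The size is modest under the trial's own assumptions, the plot is optional, and the -1 code moves little.

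Much of this limits the size, but it does not remove the mismatch. Residual checks test whether the log model fits, not whether it answers the protocol's question. A log model that fits perfectly still gives no cost difference (Step 4), and model failure has no stated criterion. The descriptive means carry no treatment contrast and no confidence interval.

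A reader might infer that the plan would report a false saving when mean costs are equal. Lognormal arms with equal means and log-SDs of 0.8 (active) and 0.6 (placebo) do give a ratio of exp(-(0.64 - 0.36)/2) = 0.87. But those SDs are chosen, not documented; the reverse pair gives 1.15. The planning scenario gives log-SDs only 0.08 apart and no reversal.

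**Conclusion.** The point holds as a mismatch between the promised quantity and the planned one. Following SAP 6.2.6 and 7.2.6 as written would produce no between-arm difference in mean cost and no ICER estimate or interval, whether or not the log model fits.

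The distortion in the ratio is likely to be modest: about 0.05 (0.85 against 0.81) under the planning scenario, falling to about 0.01 with common costs added. This rests on cost being proportional to ventilated days, deaths counted as 28 days, a 1-day floor and the assumed common costs. The true size cannot be fixed until unit costs are known. A reversal of direction is possible only in theory; nothing in the documents supports expecting one.

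The consequence is low. The analysis lies outside the hierarchy in SAP 6.1.3 and is deferred to the Day 180/360 addenda.

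**What to change.** In SAP 6.2.6 and 7.2.6:
1. Make the between-arm difference in arithmetic mean total cost, with a bootstrap 95% CI, the main cost comparison, whether or not the log model fits.
2. Form the ICER from that difference and the between-arm difference in mean VFDs with deaths as 0 (the convention in Protocol 8.10). Resample patients within arm so that cost and effect are bootstrapped jointly. Let this replace the per-patient VFDsurv plot as the cost-effectiveness result.
3. Keep the log-cost model and geometric mean ratio as a sensitivity analysis.

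This is more than reordering two methods already in the SAP. The bootstrap there names no difference, and mean VFDs are left out of the planned summaries (SAP 7.2.3.2), so two estimates are added. Intervals will be somewhat wider. Unit costs are still to be supplied, so the change can be made before any cost is analysed.

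The fix does not address a separate feature of the cost variable: a patient who dies early has 0 days free and so is costed as 28 days of each such support. That affects both scales and needs its own decision.
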